6.3.5. Efficacy Assessments

For the binary primary and secondary endpoints, subjects missing the evaluations at a given visit will be treated as failures (non-responders). No imputation of missing data will be performed for any continuous efficacy assessments.

6.4. VISIT WINDOWS

All data will be summarized according to the scheduled visit and time points as outlined in the protocol and by the visit denoted on the electronic case report form (eCRF). Further, premature withdrawal (PW) visits (through Week 48/Month 12) will be windowed

to the nearest scheduled visit based on the study day of occurrence relative to the target day of each scheduled visit according to Table 2 below.

Table 2: Visit Windows for Assigning PW Visits to a Scheduled Visit

Study Period	Visit	Target Day	Window for Reassignment to Scheduled Visit
Treatment Period	Day 1	1	1
	Week 1	8	2 - 15
	Week 3	22	16 - 25
	Week 4 (Month 1)	29	26 - 36
	Week 6	43	37 - 53
	Week 9	64	54 - 74
	Week 12 (Month 3)	85	75 - 95
	Week 15	106	96 - 116
	Week 18	127	117 - 137
	Week 21	148	138 - 158
	Week 24 (Month 6)	169	159 - 176
Follow-Up Period	Week 28 (Month 7)	197	177 - 225
	Week 36 (Month 9)	253	226 - 295
	Week 48 (Month 12)	337	≥ 296

In the event that a PW visit gets reassigned to a visit for which the subject has scheduled data collected, the data from the nominal scheduled visit will take precedence and the data from the PW visit will not be summarized.

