#### **9.5.6.8 Week 15**

- Obtain predose blood samples for hematology and glucose analysis (see [Section 9.5.4.6](#) for details concerning test results and study participation).
- Perform predose urine pregnancy test for females of childbearing potential; the pregnancy test must be negative for the subject to receive study drug.
- Enquire about signs and symptoms and concomitant medications throughout the visit.
- Collect predose vital signs. Additional vital sign monitoring may be performed in the event of infusion-associated AEs (see [Section 9.5.4.3](#) for details).
- Obtain study medication vial assignment and volume of study drug to be administered from EDC.
- Administer study drug and record date, volume and rate of infusion, and start/stop times of dosing.

Subjects will be discharged from the study center after all of the procedures have been completed and will be instructed to return to the clinic at Week 18.

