#### **9.5.6.11 Week 24/Premature Withdrawal – Treatment Period**

Week 24 is the final visit of the Treatment Period. Study drug is not administered.

- Obtain blood samples for hematology and chemistry (including thyroid, glucose, and HbA1c) analysis (see [Section 9.5.4.6](#) for details concerning test results and study participation).
- Collect urine sample for urinalysis and also for a pregnancy test for females of childbearing potential.
- Collect blood sample for immunogenicity testing (only subjects who complete the Treatment Period, not those who prematurely discontinue study drug administration).
- Collect blood sample for PK analyses (only subjects who complete the Treatment Period, not those who prematurely discontinue study drug administration).
- Enquire about signs and symptoms and concomitant medications throughout the visit.
- Perform 12-lead ECG.
- Perform physical and ophthalmic examinations, including vital signs.
- Measure weight.
- Perform efficacy assessments (CAS, Clinical Measures of Severity including proptosis, diplopia and motility restriction).
- Administer GO-QoL questionnaire.

Subjects who were proptosis non-responders in Study HZNP-TEP-301 will enter the Follow-Up Period and will be instructed to return to the clinic in one month for the first follow-up visit. Subjects who relapsed during the Follow-Up Period of HZNP-TEP-301 and chose to enter this extension study will not participate in the Follow-Up Period.

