PK samples ²³	X	X	X	X		X					X ²¹							
Contact (phone/email) to assess additional TED treatment ²⁴															X	X	X	X

ADA=anti-drug antibody; AE=adverse event; CAS=Clinical Activity Score; ECG=electrocardiogram; FT3=free triiodothyronine; FT4=free thyroxine; FU=Follow-Up; GO-QoL=Graves' Ophthalmopathy Quality of Life Questionnaire; HbA1c=glycated hemoglobin; M=month; NAb=neutralizing antibody; PK=pharmacokinetic; PW=premature withdrawal; SAE=serious adverse event; TED=thyroid eye disease; TSH=thyroid stimulating hormone; W=week.

Footnotes:

1. Open-label Treatment Period. Subjects with TED who are proptosis non-responders at Week 24 of HZNP-TEP-301 or were proptosis responders at Week 24 but who meet criteria for re-treatment due to relapse during the Follow-Up Period in HZNP-TEP-301 are eligible to enroll and receive 8 infusions of teprotumumab (10 mg/kg for the first infusion titrated to 20 mg/kg for the remaining infusions) in an open-label fashion.
2. Proptosis non-responders from Study HZNP-TEP-301 will participate in a 6-month Follow-Up Period; subjects who relapsed during the Follow-Up Period of HZNP-TEP-301 will not participate.
3. Proptosis non-responders from Study HZNP-TEP-301 who complete the Month 12 Visit and subjects who relapsed during the Follow-Up Period of HZNP-TEP-301 and complete the Week 24 Visit will be contacted via phone or email by research staff to enquire if any treatment for TED has been received since last study contact.
4. If subjects wish to discontinue study drug during the open-label Treatment Period, subjects will return for a clinic visit and undergo the Week 24 assessments, except for PK and ADA evaluations. Subjects who were proptosis non-responders at Week 24 of HZNP-TEP-301 will be encouraged to continue study participation in the Follow-Up Period.
5. If a subject wishes to prematurely discontinue from the study during the Follow-Up Period, he/she will return for a clinic visit and undergo the Month 12 assessments prior to discharge.
6. On Day 1 (Baseline), subjects will receive the first dose of study drug; however, Baseline assessments will be performed prior to dosing.
7. Day 1 will occur within 14 days after the final visit of Study HZNP-TEP-301 (Week 24 for proptosis non-responders and up to Week 72 for subjects who relapse).

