6. GENERAL ASPECTS FOR STATISTICAL ANALYSIS

6.1. GENERAL METHODS

The following conventions will be utilized in the analyses:

- In general, descriptive summaries will be provided by treatment received in HZNP-TEP-301 and overall.
- The following treatment group labels will be used: “HZNP-TEP-301 Placebo” for subjects who were randomized to Placebo in HZNP-TEP-301 and “HZNP-TEP-301 HZN-001” for subjects who were randomized to HZN-001 in HZNP-TEP-301.
- Unless otherwise indicated, continuous variables will be summarized using the number of observations (n), mean, standard deviation (SD), median, minimum (min), and maximum (max). Categorical variables will be summarized using number of observations (n), frequency and percentages of subjects.
- The same number of decimal places as the raw data will be presented when reporting min and max, 1 more decimal place than in the raw data will be presented when reporting mean and median, and 2 more decimal places than in the raw data will be presented when reporting SD.
- If multiple assessments occur at a given time point, the latest value will be used. If multiple assessments occur on the same day and the time is not recorded, the average of the values will be used in any descriptive summaries.
- All relevant subject data will be included in listings. All subjects entered into the database will be included in subject data listings.
- Additional programming considerations are provided in Section 14.

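### SAP 6.4 applies premature-withdrawal (PW) precedence to the whole visit, so PW safety results go untabulated even where the mapped visit never measured them

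*SAP*

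**What the plan says.** SAP 6.4 covers all data. It maps a PW visit "to the nearest scheduled visit based on the study day of occurrence relative to the target day of each scheduled visit", using the day ranges in its visit-window table. The precedence sentence then has a trigger and a consequence. The trigger is "In the event that a PW visit gets reassigned to a visit for which the subject has scheduled data collected". The consequence is "the data from the nominal scheduled visit will take precedence and the data from the PW visit will not be summarized". Neither part refers to individual assessments, and there is no exception for safety data.

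The PW visit is a full one. Under the notes to the SAP 3.8 schedule, subjects who stop drug in the Treatment Period are handled as follows: "subjects will return for a clinic visit and undergo the Week 24 assessments, except for PK and ADA evaluations". For a subject leaving during follow-up, "he/she will return for a clinic visit and undergo the Month 12 assessments prior to discharge". Protocol 9.5.6.11 spells out the laboratory part: "Obtain blood samples for hematology and chemistry (including thyroid, glucose, and HbA1c) analysis". It also lists urinalysis, ECG, weight, and physical and ophthalmic examinations. By contrast, the Week 15 blood draw in Protocol 9.5.6.8 reads "Obtain predose blood samples for hematology and glucose analysis".

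SAP 6.1 has a general convention for repeated values: "If multiple assessments occur at a given time point, the latest value will be used".

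**The concern.** Precedence is sensible when two values compete for one cell of a table. Here the losing value often has no competitor. One item collected at the mapped visit, such as a glucose result, is enough to keep the PW ECG, HbA1c, chemistry and eye examination out of the tables.

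The situation is foreseeable. Protocol 9.4.6.3.2 withdraws a subject from treatment if a severe drug-related event persists within 2 weeks of the next dose. With dosing every 3 weeks that point comes about 21 − 14 = 7 days after an infusion. From Week 6 onward, Days 1 to 10 after an infusion given on its target day still belong to that infusion's visit window. The documents set no interval for the PW visit, so how often it falls there is unknown.

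HbA1c shows what is at stake. Hyperglycemia is an event of special interest, yet the only scheduled post-baseline HbA1c tests in the Treatment Period are at Week 12 and Week 24 (or PW). For a subject stopping before Week 12, the PW result may be the only scheduled one in that period.

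The planned laboratory, vital-sign, ECG-shift and eye-examination tables (SAP 10.6 to 10.8 and 10.10) are by visit, and no worst-post-baseline laboratory table is planned. The QTcF threshold summary in SAP 10.10 uses any post-baseline assessment but does not say whether a PW ECG set aside under 6.4 counts.

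**Working it through.** The plan gives no figure to reproduce, so the check sets the windows against the schedule.

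**Inputs.** Target days and window limits are from the visit-window table in SAP 6.4. Assessments per visit are from the SAP 3.8 schedule, SAP 10.5, 10.6 and 10.10, and the laboratory schedule in SAP 10.8.

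**Definition.** Assume each scheduled visit takes place on its target day. A collision day is then a later day still inside that visit's window, so collision days = upper limit − target day.

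| Visit | Target | Upper limit | Collision days | PW safety items the visit does not schedule |
|---|---|---|---|---|
| Week 1 | 8 | 15 | 7 | chemistry/thyroid, HbA1c, urinalysis, ECG, weight |
| Week 3 | 22 | 25 | 3 | HbA1c, eye exam, weight |
| Week 4 | 29 | 36 | 7 | chemistry/thyroid, HbA1c, urinalysis, ECG, eye exam, weight |
| Week 6 | 43 | 53 | 10 | HbA1c, weight |
| Week 9 | 64 | 74 | 10 | HbA1c, ECG, eye exam, weight |
| Week 12 | 85 | 95 | 10 | none |
| Week 15 | 106 | 116 | 10 | chemistry/thyroid, HbA1c, urinalysis, ECG, eye exam, weight |
| Week 18 | 127 | 137 | 10 | HbA1c, ECG, weight |
| Week 21 | 148 | 158 | 10 | chemistry/thyroid, HbA1c, urinalysis, ECG, eye exam, weight |

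**Treatment Period total:** 7 + 3 + 7 + 6 × 10 = 77 days.

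Days on which the PW item has no scheduled counterpart:
- HbA1c (and weight): 77 − 10 (Week 12) = 67, or 87%.
- ECG: 7 + 7 + 10 + 10 + 10 + 10 (Weeks 1, 4, 9, 15, 18, 21) = 54, or 70%.
- Eye examination: 3 + 7 + 10 + 10 + 10 (Weeks 3, 4, 9, 15, 21) = 40, or 52%.
- Chemistry, thyroid and urinalysis: 7 + 7 + 10 + 10 (Weeks 1, 4, 15, 21) = 34, or 44%.
- Hematology, glucose and vital signs: 0, because every one of these visits schedules them.

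**Follow-Up Period:** Week 28 gives Days 198–225 (225 − 197 = 28) and Week 36 gives Days 254–295 (295 − 253 = 42), 70 in all. ECG and eye examination are scheduled at neither visit, so they are absent on all 70 days. Laboratory tests and weight are absent on the 28 Week 28 days.

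**Sensitivity to the target-day assumption.** Allowed visit windows are ±1 day at Weeks 1 and 4 and ±3 days at the other seven treatment visits. If every visit ran early by the full allowance, 2 × 1 + 7 × 3 = 23 collision days would be added; if every visit ran late, 23 would be lost. The Treatment Period total therefore lies between 54 and 100. With ±7 days at the two follow-up visits, the 70 becomes 56 to 84.

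**Example.** Week 15 is attended on Day 106 and the PW visit takes place on Day 112. Day 112 lies in the Week 15 window (96–116) and Week 15 has data, so nothing from the PW visit is summarized.

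**The case against.** The strongest reply is that nothing is lost from the record. SAP section 10 puts all safety information in listings, and the index of listings includes separate ones for out-of-range laboratory results. Adverse events are assigned by dosing dates, so the event behind a withdrawal still appears in the tables, including the one for events leading to permanent withdrawal of drug. Proptosis non-responders who stop drug are encouraged to continue into follow-up, where they are assessed again. All of this stands: the loss is from summary tables only.

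A reader might infer that the safety tables are therefore biased toward normal. The documents do not support this. They say nothing about the direction of PW values, and an ECG missing from a visit with no scheduled ECG leaves a gap in reporting; it does not shift an existing estimate. Nor can the counts be turned into an expected number of affected subjects, since the plan states neither a sample size nor a withdrawal rate. A PW visit near the next due infusion would fall in an unattended visit's window and be kept.

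A programmer could also read the trigger per assessment, so that an ECG never scheduled at Week 15 faces no competing value. That is a reasonable way to implement it, but the text does not say it.

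Finally, a reader might call 6.4 an error because it keeps the earlier value while 6.1 keeps the latest. A specific rule for reassigned PW visits can override a general convention. The SAP need only say that it does.

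The objection that per-assessment precedence would create odd rows, such as a Week 15 ECG, does not stand. The current rule already creates them whenever the mapped visit was missed.

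**Conclusion.** The point holds as a specification fault of limited reach. As written, SAP 6.4 leaves PW safety results out of the by-visit tables in cases where no scheduled value competes with them.

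With visits on target days, this can happen for at least one item on 67 of the 77 Treatment Period collision days (all but those after Week 12) and on all 70 in follow-up. It rests on the visit-level wording being programmed as it stands. For hematology, glucose and vital signs at treatment visits, only a second, later value is left out; keeping the scheduled value there is an acceptable convention. The number of subjects affected and the effect on any safety conclusion cannot be determined from the documents.

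**What to change.** In SAP 6.4, apply precedence separately for each assessment: the scheduled value is used where one exists for that parameter, and otherwise the PW value is summarized at the mapped visit. Add that PW ECGs count in the any-post-baseline QTcF categories of SAP 10.10, and that 6.4 takes precedence over the latest-value convention in 6.1 for reassigned PW visits.

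The cost is a few sentences and a small programming change. The drawback is a few sparse by-visit rows, of a kind the present rule already produces.

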6.5. POOLING OF SITES

In general, data from all sites will be summarized together for efficacy and safety analyses. Select descriptive summaries will be provided by site and region: US and EU.

6.6. SUBGROUPS

Subgroups of interest include:

- Subject enrollment type (subjects who were proptosis non-responders in HZNP-TEP-301, subjects who relapsed during the Follow-Up Period of HZNP-TEP-301)
- Tobacco use status at time of randomization in HZNP-TEP-301: Tobacco uses of “never” and “former” will be grouped as tobacco non-users, and tobacco uses of “current” will be considered tobacco users as collected on the HZNP-TEP-301 substance use eCRF (non-user, user)

- Region (US, EU)
- Site
- Age (<65 years, ≥65 years) calculated using the HZNP-TEP-302 study informed consent date.
- Gender (male, female)
- Race (white, black or African American, Asian, other)
- Ethnicity (Hispanic or Latino, not Hispanic or Latino)

Descriptive summaries will be provided for various efficacy endpoints and TEAEs for select subgroups as specified in Section 8 [and Section 10.3, respectively](#). If one of the subgroups has fewer than 5 subjects, no summary table will be created for that subgroup, except for site. Sites will not be pooled regardless of subject counts in the by-site subgroup analyses.

7. DEMOGRAPHIC, OTHER BASELINE CHARACTERISTICS, MEDICATION AND PROTOCOL DEVIATIONS

7.1. SUBJECT DISPOSITION AND DISCONTINUATION

A summary of subject disposition will be provided including the number of subjects screened and the number and percent of screen failures. Further, the number and percent of subjects enrolled overall and by subject enrollment type (proptosis non-responders in HZNP-TEP-301 and subjects who relapsed during the Follow-Up Period of HZNP-TEP-301) will be provided, as well as the number of subjects in each analysis population (ITT and PK Population). In addition, the number and percent of subjects in each of the following categories will be provided:

- Completed the Treatment Period
- Discontinued early from the Treatment Period
 - Proptosis non-responder in HZNP-TEP-301 and did not continue in the Follow-Up Period with reasons for discontinuations
 - Proptosis non-responder in HZNP-TEP-301 and continued in Follow-Up Period with reasons for discontinuation Subjects who relapsed in HZNP-TEP-301
- Had any data collected during the Follow-Up Period
- Completed the study
 - Completed the Treatment Period and Follow-Up Period for subjects who were proptosis non-responders in HZNP-TEP-301
 - Discontinued from the Treatment Period but completed the Follow-up Period for subjects who were proptosis non-responders in HZNP-TEP-301
 - Completed the Treatment Period for subjects who relapsed during the Follow-Up Period of HZNP-TEP-301
- Discontinued early from the study by reason for discontinuation (Did not complete the Treatment Period and did not continue in the Follow-Up Period for subjects who were proptosis non-responders in HZNP-TEP-301; did not complete the Treatment Period, continued in the Follow-Up Period, but did not complete the Follow-Up Period for subjects who were proptosis non-responders in HZNP-TEP-301; completed the Treatment Period and did not continue in the Follow-Up Period for subjects who were proptosis non-responders in HZNP-TEP-301; completed the Treatment Period, continued in the Follow-Up Period but did not complete the Follow-Up Period for subjects who were proptosis non-responders in HZNP-TEP-

301; did not complete the Treatment Period for subjects who relapsed during the Follow-Up Period of HZNP-TEP-301)

- o Reasons for discontinuation

Percentages will be based on the number of subjects in the ITT Population.

Subject disposition information will be summarized by treatment received in HZNP-TEP-301 and overall.

A separate summary will be provided of the number and percentage of subjects attending each visit and participating in each Follow-Up contact. Percentages will be based on the ITT Population.

7.2. DEMOGRAPHIC AND OTHER BASELINE CHARACTERISTICS

Demographic and other baseline characteristics will be based on information obtained on Study Baseline (Day 1 of HZNP-TEP-302, or the last measurement available in the HZNP-TEP-301 study if measurement on Day 1 of HZNP-TEP-302 is not available). Descriptive summaries of demographic and baseline characteristics will be presented overall and by treatment received in HZNP-TEP-301 study based on the ITT Population. These characteristics include study eye (right, left) as identified in HZNP-TEP-301, age, age category (<65 years, ≥65 years), gender, race, ethnicity, height, weight, body mass index, region (US, EU), tobacco use status as randomized in HZNP-TEP-301 (non-user, user), actual tobacco use status as collected on the substance use CRF in HZNP-TEP-301 (non-user, user), tobacco use history (never, current, former), alcohol use history (never, current, former), child-bearing potential (yes, no, not applicable), time since diagnosis of Graves' disease and time since diagnosis of TED. Further, baseline levels of free triiodothyronine (FT3), free thyroxine (FT4), thyroid stimulating hormone (TSH) and glycated hemoglobin A1C (HbA1C) will be summarized.

Age will be calculated as: (informed consent date of HZNP-TEP-302 - date of birth + 1) / 365.25 and truncated to complete years. Missing data imputation rules are provided in Section 6.3.1.

Weight will be converted to kilograms (kg) when reported in pounds (lbs) as follows:
Weight (in kg) = weight (in lbs) * 0.4536

Time since Graves' disease diagnosis (years) will be calculated as: (first dose date of HZNP-TEP-302 - date of diagnosis + 1) / 365.25, rounded to two decimal places. Missing data imputation rules are provided in Section 6.3.2.

Time since TED (months) will be calculated as: (first dose date of HZNP-TEP-302 - date of diagnosis + 1) / 30.4, rounded to two decimal places. Missing data imputation rules are provided in Section 6.3.2.

Separate summaries will be provided by tobacco use (non-user, user) and region (US, EU) for the ITT Population. Demographic data and baseline characteristics will be provided in subject listings.

7.3. MEDICAL HISTORY

Medical history will be based on information collected in HZNP-TEP-301 study. Medical history information will be coded using Medical Dictionary for Regulatory Activities (MedDRA) version 20.1 and summarized by treatment received in HZNP-TEP-301 and overall in the ITT Population. Summaries will be ordered alphabetically by system organ class (SOC) and then, within a SOC, alphabetically by preferred term (PT). Medical history will be provided in subject listings.

7.4. MEDICATION

Medications will be coded using World Health Organization Drug Dictionary (WHO-DD) September 2017. Prior and concomitant medications will be summarized by presenting the counts and percentage of subjects using medications overall and by treatment received in HZNP-TEP-301 for the ITT Population. Summaries will be provided by Anatomical Therapeutic Chemical (ATC) Level 4 term and PT. Medication summaries will be sorted alphabetically by ATC Level 4 and by PT within ATC Level 4. Subjects will be counted only once for each medication class and each preferred drug name.

Prior and concomitant medications will be listed together with a designation to identify the medications as prior and/or concomitant and sorted by start date. Separate listings will be provided for thyroid eye disease medications and medications taken for other indications.

7.4.1. Prior Medication

Prior medications will be presented separately from concomitant medications in a summary table. Any medication with a start date prior to the date of first dose in study HZNP-TEP-301 will be considered a prior medication. Missing date imputation rules are provided in Section 6.3.3.

